**Table 3: Sexual Function Questionnaire Outcomes and Coding**

Subject's Answer	Code
Not at all	1
Seldom, less than 25% of the time	2
Sometimes, about 50% of the time	3
Usually, about 75% of the time	4
Always	5
The problem stops your sexual activity	6

All variables given above will be summarized using frequency and percentage by visit and outcome categories. Unscheduled visits will be grouped with the associated visit (e.g., visit 3.1 will be included with visit 3).

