9.10 Other Endpoints

9.10.1 Subject Satisfaction

Subject satisfaction with the study drug and subject sexual satisfaction will be summarized using frequency and percentage.

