Appendix E: Sexual Function Questionnaire

How frequently in the PAST MONTH have you had the problems listed below?* **ALSO**, MARK THE BOX IN THE LAST COLUMN if the problem stops your sexual activity.

		Not at all	Seldom, less than 25% of the time	Sometimes, about 50% of the time	Usually, about 75% of the time	Always	MARK THE BOX IF THE PROBLEM STOPS YOUR SEXUAL ACTIVITY
a.	Vaginal dryness during sexual activity	1	2	3	4	5	
b.	Lack of sexual interest or desire	1	2	3	4	5	
c.	Vaginal tightness	1	2	3	4	5	
d.	Pain during penetration or intercourse	1	2	3	4	5	
e.	Anxiety about your sexual performance	1	2	3	4	5	
f.	Unable to orgasm	1	2	3	4	5	
g.	Vaginal bleeding or irritation from penetration or intercourse	1	2	3	4	5	
h.	Increased sensitivity of your skin to intimate touching	1	2	3	4	5	
i.	Sharp pain inside or outside your vagina	1	2	3	4	5	
j.	Other problem with sexuality; Please specify:	1	2	3	4	5	

*Source: Question 10, Sexual Function Questionnaire, Fred Hutchinson Cancer Research Center.

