### 4.2 General Presentation Considerations

This section details general policies to be used for the statistical analyses. Deviations from these general policies may be given in the specific detailed sections of this statistical analysis plan. When this situation occurs, the rules set forth in the specific section take precedence over the general policies. The following policies will be applied to all data presentations and analyses:

- All statistical tests will use a 2-sided significance level of  $\alpha = 0.05$ .
- Summary statistics will consist of the number and percentage of responses in each category for discrete variables, and N, mean, median, standard deviation (SD), minimum, and maximum for continuous variables.
- All mean and median values will be formatted to one more decimal place than the measured value. SD will be formatted to two more decimal places than the measured value.
- All percentages will be rounded to one decimal place. The number and percentage of responses will be presented in the form XX (XX.X), where the percentage is in the parentheses. The decimal of the percentage may be dropped due to space constraints when creating a table. The denominator for percentage calculations will be the number of non-missing observations.
- All listings will be sorted for presentation in order of site number, subject number, and date of procedure or event.
- When necessary for analysis purposes, partial dates will be completed (i.e., turned into complete dates) using the most conservative approach.
- All analysis and summary tables will have the population sample size in the column heading.
- Baseline is defined as the last non-missing measurement taken on (prior to treatment) or before enrollment.
- Calculating change from baseline to a visit will be done as follows:  $\text{Change} = \text{Visit} - \text{Baseline}$
- Version 9.4 of SAS or higher will be the statistical software package used to produce all summaries, listings, statistical analyses, and graphs.

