#### 4.9.2 Sexual Function Questionnaire

The Sexual Function Questionnaire has 10 variables:

1. Vaginal dryness during sexual activity
2. Lack of sexual interest or desire
3. Vaginal tightness
4. Pain during penetration or intercourse
5. Anxiety about your sexual performance
6. Unable to orgasm
7. Vaginal bleeding or irritation from penetration or intercourse
8. Increased sensitivity of your skin to intimate touching
9. Sharp pain inside or outside your vagina
10. Other problem with sexuality

The outcomes and coding for these 10 Variables are provided in Table 3.

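### SAP Table 3 puts the separate tick-box for problems that stop sexual activity in the same variable as the 1–5 frequency answer, so a woman who gives both answers cannot be coded as she replied

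*SAP*

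**What the plan says.** Protocol Appendix E asks "How frequently in the PAST MONTH have you had the problems listed below" and prints five answers, numbered 1 (Not at all) to 5 (Always), for items a to j. It then adds a second instruction for the same items: "MARK THE BOX IN THE LAST COLUMN if the problem stops your sexual activity". That instruction is introduced by the word ALSO, and the box has no number on the form.

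SAP 4.9.2 states that "The Sexual Function Questionnaire has 10 variables", one for each item, and that "The outcomes and coding for these 10 Variables are provided in Table 3". Table 3 is a single list of answers and codes. It runs from 1 to 5 as on the form and then gives "The problem stops your sexual activity" the code 6. The planned output is described in one sentence: "All variables given above will be summarized using frequency and percentage by visit and outcome categories". The general rule in SAP 4.2 is that "The denominator for percentage calculations will be the number of non-missing observations".

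Neither document defines a separate variable for the box or gives a rule for a woman who marks a frequency and also ticks it.

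**The concern.** The form treats frequency and impact as two questions. Sometimes plus a tick is a complete and valid reply. The SAP gives that reply one variable and two eligible codes. If code 6 takes precedence, the woman disappears from her frequency row. If both codes are kept, she appears twice in one column.

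The table is laid out by visit, so readers will compare baseline with visits on treatment. If ticks replaced frequencies and more women ticked the box on treatment, the frequency rows would fall with no woman having changed her frequency answer. That would look like an improvement caused by greater functional impact. Placing the box above Always also suggests an order that the form does not have, since a problem that occurs seldom can still stop sexual activity.

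**Working it through.** The plan states no figure on this point, so there is none to reproduce. The check has two parts.

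**1. Instrument against coding**

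| | Protocol Appendix E | SAP 4.9.2 and Table 3 |
|---|---|---|
| Responses per item | Two: frequency and box | One variable |
| Frequency codes | 1–5 | 1–5 |
| Box | Separate column, no number | Code 6 in the same list |
| Both marked | Allowed, beside any frequency | No rule |

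Ten items with two responses each need 20 variables; the SAP defines 10.

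**2. What each reading would print**

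Let N be the women answering an item, n_k those choosing frequency k, t_k those among the n_k who also tick, and T the sum of the t_k.

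- (a) Tick replaces frequency: row k = (n_k − t_k)/N, row 6 = T/N.
- (b) Both kept, women as denominator: row k = n_k/N, row 6 = T/N, column sum = (N + T)/N.
- (c) Both kept, responses as denominator: row k = n_k/(N + T), row 6 = T/(N + T).

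The counts below are assumed, because the documents give none: N = 100, answers 50/20/15/10/5 across codes 1–5, and T = 8, made up of 5 of the Usually group and 3 of the Always group.

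| Reading | Codes 1 / 2 / 3 / 4 / 5 / 6 (%) | Column sum | Usually or Always |
|---|---|---|---|
| (a) | 50 / 20 / 15 / 5 / 2 / 8 | 100% | (15 − 8)/100 = 7% |
| (b) | 50 / 20 / 15 / 10 / 5 / 8 | 108/100 = 108% | 15/100 = 15% |
| (c) | 46.3 / 18.5 / 13.9 / 9.3 / 4.6 / 7.4 | 100% | 15/108 = 13.9% |

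Range over T, with all ticks in the Usually and Always rows:

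- T = 0: all three readings give 15%.
- T = 15: (a) gives 0/100 = 0%; (b) gives 15% with a column sum of 115%; (c) gives 15/115 = 13.0%.

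The position of the ticks matters as well. If all 8 fall in the Sometimes row, reading (a) leaves Usually or Always at 15% and lowers Sometimes from 15% to (15 − 8)/100 = 7%.

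With frequency and box held apart, the same data give 50/20/15/10/5, which sums to 100%, and a separate box result of 8/100 = 8%.

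**The case against.** The strongest reply is that the SAP never says code 6 displaces codes 1–5. It asks only for counts and percentages by category. Where this SAP wants mutually exclusive categories it says so, as in the compliance categories of section 4.6; that wording is absent from 4.9.2. Five frequency rows plus a sixth row counting ticks, with women as denominator, would fit the text. The frequency rows would then be intact, and a footnote could explain the column sum.

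Much of this stands. A reader might infer that the SAP discards frequency answers and so understates frequent pain, dryness and bleeding at every visit. The documents do not support that:

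- Replacement is only one of the possible readings.
- A tick may sit beside any frequency, so the affected rows need not be Usually and Always.
- The schedule places the sexual satisfaction questionnaires at Visits 2–5, not at Screening or the telephone contact.
- No individual percentage could exceed 100%; only the column sum could.

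The consequence is also small. Protocol 9.10.1 plans only that "Subject satisfaction with the study drug and subject sexual satisfaction will be summarized using frequency and percentage", and the SAP specifies no score, test or change from baseline for these items. Listing 16.3.2 covers the questionnaire. Vaginal pain in the eDiary and unexpected vaginal bleeding as an adverse event are captured separately and do not depend on Table 3.

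What the reply does not remove is the coding. One variable with one code list cannot hold two valid answers from the same woman. The harmless table requires the programmer to store the box elsewhere, which the SAP does not provide for.

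**Conclusion.** The coding in Table 3 is wrong as written, not merely short of detail: it merges two responses that the form keeps apart. A woman with both answers either loses her frequency answer, which understates whichever rows the ticked women belong to, or is counted in two categories. In the second case the column sums to more than 100%, or every frequency percentage is diluted if responses are the denominator. The SAP does not choose, and its non-missing rule does not settle whether an observation is a woman or a response.

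The mismatch follows from the text alone. Its numerical effect rests on assumed counts: between no change and complete loss of the Usually and Always rows in the example, depending on the tick rate, where the ticks fall and which reading is programmed. The effect is limited to exploratory descriptive Table 14.3.5.18 in the Safety population at Visits 2–5. The primary analysis, power and type I error are untouched. This is a low-severity correction.

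**What to change.** - Remove code 6 from SAP Table 3 and keep codes 1–5 as the frequency variable for each of the ten items.
- Add one yes/no variable per item for the box. State in 4.9.2 that a tick does not replace the frequency answer.
- Tabulate the box separately from the frequency, and name the women who answered the item as the denominator for both.
- A cross-tabulation of box by frequency is optional.

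The cost is an edit to Table 3 and its paragraph and a change to one table shell. No new data are needed if the database holds both responses as Appendix E collects them. The sponsor should confirm that, because a capture field built on Table 3 might have stored only one of the two.

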### 4.9.1 Subject Satisfaction Questionnaires

Four endpoints will be defined for Subject Satisfaction Questionnaires:

- Satisfaction level to study product which will be evaluated at baseline and visit 3-5 based on the answers to question “how satisfied were you with your most recent/study birth control method”:
  - a. Very satisfied
  - b. Satisfied
  - c. Somewhat satisfied
  - d. Somewhat dissatisfied
  - e. Dissatisfied
- Likelihood of recommendation as a vaginal contraceptive gel which will be evaluated at Visit 3-5 with outcome:
  - f. Very likely
  - g. Likely
  - h. Somewhat likely
  - i. Somewhat unlikely
  - j. Unlikely
- Likelihood of recommendation as another birth control option which will be evaluated at Visit 3-5 with outcome:
  - k. Very likely
  - l. Likely
  - m. Somewhat likely
  - n. Somewhat unlikely
  - o. Unlikely
- Likelihood to continue use which will be evaluated at Visit 3-5 with outcome:
  - p. Very likely

- q. Likely
- r. Somewhat likely
- s. Somewhat unlikely
- t. Unlikely

All four endpoints will be summarized using frequency and percentage by visit and outcome level. Unscheduled visits will be grouped with the associated visit (e.g., visit 3.1 will be included with visit 3).

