#### 4.9.3 Sexual Satisfaction and Lubrication

Sexual Satisfaction and Lubrication will be assessed with the following questions, asked at baseline and at each subsequent visit:

- Baseline: What impact did your most recent contraceptive method have on your sex life in the last 4 weeks of use?
- Visit 3-5: What impact has the study contraceptive method had on your sex life since your last study visit?

The response set for these questions is as follows:

- a. My sex life was a lot better than before
- b. My sex life was a little better than before
- c. My sex life was no different than before
- d. My sex life was a little worse than before
- e. My sex life was a lot worse than before

The Female Sexual Function Index (FSFI), a 19-item questionnaire, provides scores on six domains of sexual function (desire, arousal, lubrication, orgasm, satisfaction, and pain) as well as a total score. Only question 10 from the FSFI will be summarized according to the following response set:

- 10. Over the past 4 weeks, how difficult was it to maintain your lubrication ("wetness") until completion of sexual activity or intercourse?
  - u. No sexual activity
  - f. Extremely difficult or impossible
  - g. Very difficult
  - h. Difficult
  - i. Slightly difficult
  - j. Not difficult

All variables given above will be summarized using frequency and percentage by visit and outcome categories. Unscheduled visits will be grouped with the associated visit (e.g., visit 3.1 will be included with visit 3).

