#### 4.11 Pregnancy Intendedness

The pregnancy intendedness scale and its change from the baseline will be summarized descriptively by visit. Unscheduled visits will be grouped with the associated visit (e.g., visit 3.1 will be included with visit 3).

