##### 4.11.1 Determination of Sample Size

Simulation methods are used to evaluate the likelihood of various sample sizes providing enough information to test the primary hypothesis (one-sided Type 1 error of 0.025) and enough use cycles of Amphora gel to address other regulatory requirements. The six month (183 d) cumulative pregnancy percentage was estimated using Kaplan-Meier methods.

The sample size determination assumes the following:

- Study drug pregnancy percentage: 16.5%
- 26.5% of subjects fail to qualify for the primary efficacy analysis population
- Of the subjects that qualify for the primary efficacy analysis population, the average number of evaluable efficacy cycles per subject: 3.17
- Exponential hazard for:
  - Pregnancy rate first 6 months: 16.5%
  - Drop out month 1: 10%
  - Drop out months 2-6: 38%

With 1349 participants aged 18 through 35 years (inclusive), the study will have 90% power to ensure that the upper limit of the 95% CI of the cumulative seven-cycle pregnancy rate is less than or equal to 21%. The expected number of completers is 515 and the expected number of cycles evaluable for safety is at least 3143.

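### Sexual Function Questionnaire items and FSFI question 10 have a true pre-gel baseline, but the SAP tabulates only percentages per visit, so it cannot show how many women newly developed or lost a problem

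*SAP*

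**What the plan says.** SAP 4.9.2 (with its Table 3) and SAP 4.9.3 use the same sentence for the ten Sexual Function Questionnaire items, the sex-life impact item and FSFI question 10: "All variables given above will be summarized using frequency and percentage by visit and outcome categories". SAP 4.9.1 does likewise for the satisfaction items: "All four endpoints will be summarized using frequency and percentage by visit and outcome level". Protocol 9.10.1 asks for no more: "Subject satisfaction with the study drug and subject sexual satisfaction will be summarized using frequency and percentage". Under SAP 4.2, "The denominator for percentage calculations will be the number of non-missing observations". The population is the Safety population.

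A pre-gel answer exists. The schedule of assessments in both documents places the questionnaires at Enrollment and Visits 3, 4 and 5, and Protocol 5.1.2 has them given at the visit where gel is first dispensed. SAP 4.9.3 describes its questions as "asked at baseline and at each subsequent visit".

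Elsewhere the SAP does use each woman's own baseline: laboratory shifts (4.8.8), improved/no change/worsened for the gynecological examination (4.8.6) and wet mount (4.8.5), change in vital signs (4.8.9), and, for another exploratory questionnaire, "The pregnancy intendedness scale and its change from the baseline will be summarized descriptively by visit" (4.11).

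**The concern.** A distribution per visit answers the question of what share of today's respondents report a problem. In a single-arm study of a vaginal gel, the more useful question is how many women who did not have dryness or tightness before the gel have it now, and how many lost it. The planned tables cannot answer that, for two reasons.

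- **Composition.** The denominator shrinks as women leave. If women with a problem leave sooner, the percentage falls although no woman improved. If they leave later, it rises.
- **Cancellation.** Even with no dropout, new problems and resolved problems offset each other in the marginal percentages.

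At stake is the reading of exploratory tolerability data. Sample size, alpha and the contraceptive efficacy conclusion are not involved.

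**Working it through.** **1. Which items have a like-for-like baseline.**
- Ten Sexual Function Questionnaire items (Protocol Appendix E) and FSFI question 10 (Appendix F): same question at every visit. The point applies in full.
- Satisfaction and sex-life impact (Appendices C and D): the baseline answer concerns the previous contraceptive method. A shift would compare methods and would not show a new or resolved problem.
- The two recommendation items and the continue-use item: no baseline. Only the composition point applies.

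**2. The plan's own attrition figures (SAP 4.11.1).** Inputs: 1349 enrolled, 26.5% not qualifying for the primary efficacy population, 3.17 evaluable cycles per qualifying woman, dropout 10% in month 1, and "Drop out months 2-6: 38" percent.
- Qualifying: 1349 × 0.735 = 991.5.
- Cycles: 991.5 × 3.17 = 3143.1 (stated: 3143).
- Completers: 991.5 × (1 − 0.10 − 0.38) = 515.6 (stated: 515). This route is inferred, because 991.5 × 0.62 × 0.835 = 513.3 is also close.

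The illustration below reads the two dropout figures as sequential, 0.90 × 0.62 = 0.558 retained at month 6. This is the milder reading, since the additive one gives 0.52.

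**3. Retention at Visit 4.** Visit 4 falls in the fifth or sixth study cycle. I take month 4.6 (five 28-day cycles, an assumption). The monthly hazard after month 1 is −ln(0.62)/5 = 0.0956. Retention = 0.90 × exp(−0.0956 × 3.6) = 0.638.

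**4. Composition effect at Visit 4.** Assume 20% have a problem at baseline, no woman's answer ever changes, and women with the problem leave at HR times the hazard of the others. Neither the 20% nor the HR is in the documents. Solve 0.8·e^(−h) + 0.2·e^(−HR·h) = 0.638 for h. The Visit 4 percentage is then 0.2·e^(−HR·h)/0.638.

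| HR | h | Visit 4 percentage | Apparent fall (points) |
|---|---|---|---|
| 1.1 | 0.441 | 19.3% | 0.7 |
| 1.25 | 0.429 | 18.3% | 1.7 |
| 1.5 | 0.412 | 16.9% | 3.1 |
| 2 | 0.384 | 14.6% | 5.4 |
| 3 | 0.345 | 11.1% | 8.9 |

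Timing matters little. Placing the visit anywhere from month 3.5 to month 5.0 gives a fall of 2.4 to 3.3 points at HR 1.5 and 7.1 to 9.5 points at HR 3.

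**5. Visit 5, allowing for exit questionnaires.** Let a be the share of leavers who answer at exit, and assume their answers are tabulated under Visit 5. With S1 the retention of women with the problem, the percentage is 0.2·[S1 + a(1 − S1)]/(0.558 + 0.442a). Solving step 4's equation at 0.558 gives S1 = 0.448 for HR 1.5 and 0.255 for HR 3.
- a = 0.5: 18.6% and 16.1%, falls of 1.4 and 3.9 points.
- a = 0.75: 19.4% and 18.3%, falls of 0.6 and 1.7 points.
- a = 0: 16.1% and 9.1%, larger than at Visit 4 because more women have left.

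The effect is therefore smaller at Visit 5 only to the extent that early leavers do answer.

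**6. Cancellation, with no dropout at all.** Take 515 women with both answers, of whom 103 (20%, assumed) report the problem at each visit. If k women are newly affected, k must have resolved. The by-visit table is identical for every k from 0 to 103. A shift table would show k directly.

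**The case against.** The case for leaving the plan alone has real weight.

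- **The endpoints are exploratory and descriptive.** The SAP does what Protocol 9.10.1 asks, and neither document attaches a hypothesis or a claim of improvement to these tables. This stands, and it limits the point to a minor one.
- **There are other routes for new symptoms.** A reader might infer that baseline questionnaires are the only way to learn whether problems began on gel. The documents do not support that. Vaginal burning, itching, pain and other symptoms are recorded in the eDiary at each use, and unexpected bleeding is an adverse event (Protocol 5.4.3). Treatment emergence is defined as onset or worsening after a dose (Protocol 5.4.2). SAP 4.8.3 tabulates eDiary symptoms by onset, severity and duration, and SAP 4.8.2 compares completers with non-completers on adverse events. What remains is dryness, tightness and lubrication, which are not named eDiary symptoms, although the other-symptoms category could catch some of them.
- **Exit questionnaires.** Early leavers are asked to undergo the exit procedures, which include the questionnaires (Protocol 6.4 and 5.1.4). This reduces the composition effect at Visit 5. It does not remove it, because women lost to follow-up give no answer, and it does nothing for Visit 4 or for cancellation.
- **The size rests on assumed inputs.** That is correct. At hazard ratios of 1.1 to 1.25 the Visit 4 fall is under 2 points. The cancellation argument does not depend on these inputs.
- **A shift table in women with both answers still misses those who leave without answering.** This is true, and it is the reason to report the number answering beside it.

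**Conclusion.** The point holds as a minor analysis gap for the ten Sexual Function Questionnaire items and FSFI question 10. The planned percentages cannot separate change in respondents from change in women, and they cannot give the number newly affected or resolved.

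The composition effect is an illustration: about 1 to 9 points at Visit 4, given 20% baseline prevalence, hazard ratios of 1.1 to 3, the SAP's dropout inputs read sequentially, and Visit 4 at about month 4.6. At Visit 5 it is 1.4 to 3.9 points for hazard ratios of 1.5 to 3 if half of the leavers answer. A reader might infer that the tables will show a false improvement. The documents give no information on which women leave, so neither the size nor the direction is established. A reader might also extend the point to every satisfaction item, but those have either no baseline or one that concerns a different method.

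A smaller labelling matter remains in SAP 4.9.1: "Satisfaction level to study product which will be evaluated at baseline and visit 3-5" names the study product, whereas the baseline question is about the previous method. The SAP does quote both versions of the question, so this needs only a clear label in the table.

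**What to change.** - **SAP 4.9.2 and 4.9.3:** keep the planned frequencies and show the number answering at each visit. For each Sexual Function Questionnaire item and FSFI question 10, add a baseline-to-visit shift table in women with both answers, giving the numbers newly affected or worse, unchanged, and improved.
- **Coding, to settle first:** Protocol Appendix E has a separate tick for a problem that stops sexual activity, but SAP Table 3 makes it an exclusive sixth code, which would overwrite the frequency answer. Analyse it as its own yes/no variable. For FSFI question 10, show the no-sexual-activity answer as its own unranked category, outside the better/worse classification.
- **SAP 4.9.1:** label the baseline satisfaction answer as referring to the previous method. A cross-tabulation of previous-method rating against gel rating is optional.

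The cost is a few more descriptive tables from data already collected, with no change to instruments, sample size, alpha or power. The remaining limitation is that women who leave without answering are still not represented.
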